10.2 Visit 2 – second hospital encounter: Following stabilization of the acute medical condition(s) for which they presented, the Veteran (and caregiver if the Veteran agrees) will be interviewed and examined by the study's PI or trained advance care practitioner using a standardized checklist of signs and symptoms of TD. We will delay this portion of the assessment until the primary treating team affirms their acute condition has stabilized to avoid misclassification of symptoms from the acute illness with those of TDD. In most cases we anticipate this will occur just prior to hospital discharge. For Veterans with symptoms suggestive of TD, we will provide a prescription for thiamine replacement 100 mg orally daily for two weeks (see **Standardized physical examination and related data**).

Nutritional history: Study personnel will perform a dietary history to adequacy of thiamine intake, recent changes in appetite, food intake or any social or medical risk factors for malnutrition. We will review medical records for acute and chronic medical illnesses that may predispose to malnutrition.

Symptom and function survey: The patient interviews will include questions about the following: acute or worsening symptoms in the following categories: neuropsychiatric (including memory loss, personality or behavior change, psychosis, mood changes, seizures), polyneuropathy (to include muscle weakness, loss of deep tendon reflexes, neuropathic pain, or sensory loss), GI dysfunction (including dysphagia, anorexia, nausea, vomiting, gastroparesis, or constipation), and cardiovascular manifestations (such as palpitations, tachycardia, dyspnea, pulmonary or peripheral edema). We will review recent trends in ability to carry out Basic Activities of Daily Living (ADLs) and Instrumental Activities of Daily Living (IADLs). We will determine if there are symptoms of adult failure to thrive such as weight loss, decreased appetite, inactivity, poor nutrition, depression, loss of functional status as defined by loss of ability to do ADLs or IADLs. We will also ask about medication compliance with both prescribed and over the counter medications and supplements.

Standardized physical examination and related data: We will perform targeted exams for signs of TDDs including mental status exam using the Montreal Cognitive Assessment (MoCA); delirium screen using the 4AT

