10.3 Visit 3 – follow-up of symptomatic Veterans after empiric thiamine treatment. All Veterans with low biomarkers OR low normal biomarkers and clinical symptoms of TDDs that were initiated on replacement will be seen at a follow-up visit 3 after two weeks of thiamine replacement. We will repeat the symptom and function survey and repeat the standardized physical assessment. We will categorize changes in symptoms and signs as *no or minimal improvement, or noticeable improvement*. We will re-order thiamine biomarkers to assess for increases in levels. We will recommend continued dosing with thiamine 100 mg daily thereafter for any Veteran with improvement in their symptoms and update their medical record to include thiamine deficiency in their problem list. If a participant failed to complete the 2 weeks of replenishment, we will provide another 2-week course of replenishment and reschedule this visit.

Study Duration/ Study Timeline:

See Table 3. We expect visit 1 will not take substantial time for the Veteran. Visits 2 and 3 will take between 60 and 90 minutes each. For Veterans without symptoms of TD, their participation will be complete after visit 2, before discharge from the hospital. For Veterans with symptoms of TD their participation will be complete after taking thiamine for 2 weeks and attending visit 3. We anticipate the study will end 24 months.

Study Endpoints:

Our primary endpoint will be determining prevalence of TD in our Veteran population. We do not anticipate stopping the study before 300 Veterans are recruited. Thiamine supplements are very safe with few side effects, so we do not anticipate stopping early for safety concerns.

Study Locations:

The study will be conducted at the VA Sierra Nevada Healthcare System Hospital inpatient units at [name]. Follow up visits will occur on the ground floor of the hospital in the research department exam rooms.

International Research:

We will not be conducting this research in international locations.

Participant Compensation:

Those that agree to participate will be compensated \$30 for visits 1 and 2 and \$200 if they attend visit 3 after discharge.

Economic Burden to Participants:

Veterans will not incur any costs because of participating in this study. Those that attend the follow up visit will incur the cost of transportation, but this will be mitigated by the \$200 compensation.

Risk to Participants:

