The principal risks to the patient are those associated with phlebotomy, namely discomfort and bruising associated with a needle stick. All efforts will be made to combine our tests with routine phlebotomy draws ordered by the primary treatment team. In some cases, additional time spent with investigators performing interviews and physical exams may cause psychological distress. In cases where thiamine is prescribed to treat suspected thiamine deficiency, there are rare instances of adverse reaction to parenteral thiamine such as anaphylaxis, pruritis, and local inflammation. Oral thiamine is typically well tolerated, the main difficulty is possibly having trouble swallowing tablets. There are extremely rare instances of side effects such as flushing, hives, itching, weakness, sweating, nausea and restlessness.

Protection Against Risk: The risk of bleeding or bruising due to phlebotomy will be mitigated by combining our specimen collection with routine collections placed by the primary treatment team to avoid extra phlebotomy. Only qualified personnel will draw blood. For psychological stress suffered, the Veterans will be assured they may refuse and withdraw from the study at any time if it becomes too burdensome. For instances where parenteral thiamine is ordered, it will be in a hospital setting where prompt medical attention is available should anaphylaxis or other side effects occur. For Veterans prescribed oral thiamine replacement who have difficulty swallowing tablets, a pill crusher will be provided. Any adverse reactions to parenteral or oral thiamine repletion will be recorded and replenishment discontinued.

Confidentiality Risks: Every effort will be made to keep all research information obtained from blood samples confidential, but absolute confidentiality cannot be guaranteed. Laboratory data obtained from blood samples will appear in the medical record for review by VA medical providers. The research information obtained as a result of participation in this study will be included in the medical record and may be given to primary care doctors. Information from which participants may be personally identified will be maintained in a confidential, locked file and will not be disclosed to third parties except with participant permission or as may be required by law.

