Thiamine repletion is considered very safe with extremely rare side effects (less than 1%) as such we do not anticipate and serious adverse events. Side effects of intravenous thiamine are reported to be flushing, restlessness, sweating, itching, hives, nausea, gastrointestinal bleeding, anaphylaxis, angioedema, weakness, and pulmonary edema. Oral thiamine (the formulation used in this study) may have similar side effects although far less commonly than the rare effects noted with IV thiamine. Thiamine is an approved treatment for Wernicke's encephalopathy and has been used widely in medical practice since the 1950's. We will not be using any new formulations or doses outside of current recommendations for the treatment of symptoms of thiamine deficiency. The PI, study coordinator, and Health Systems Specialist will monitor Veterans prescribed thiamine repletion and report any new or unusual symptoms to the IRB.

Data and Specimen Banking

During screening and recruitment, data will be on paper and stored in the research department in a locked cabinet behind locked department doors, building 1 room C3334. Only the PI and study personnel will have access to these records. Once a veteran agrees to participate and is enrolled in the trial, all subsequent data will be stored electronically on the restricted research drive. For veterans who are screened but not enrolled, their records will be maintained for 7 years in accordance with VHA Records Control Schedule (RCS 10-1). All study data will be stored both on paper in locked filing cabinets and electronically in the data collection tool REDCap. We will not be storing any specimen.

Data will be stored electronically in \\r01renhsm01.r01.med.va.gov\research\Principal Investigators\[name]\Thiamine Research and in REDCap (varedcap.rcp.vaec.va.gov). Data that will be stored electronically include:

1. Unique study ID number with patient name and last 4 of social security number and telephone number in a master key spreadsheet, to be separated from the remainder of the data.

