2. Remainder of data stored in the database include the unique study ID, age, sex, race, ethnicity, all lab results (as described in Procedures section 10.1), nutrition screening results (as described in Procedures section 10.2), symptom and function survey (section 10.2) and physical exam findings (section 10.2). For symptomatic veterans who are started on thiamine repletion, the symptom and function survey and physical exam findings will be repeated at visit 3 and recorded in the database.

Paper records of data include:

1. Patient name and hospital room number.
2. All study data will be recorded on paper and stored in locked file cabinets within the locked research department.

Sharing of Results with Participants

Thiamine and other micronutrient results will be shared with Veteran participants and will be available for them to view in their electronic medical record. For Veterans found to have low thiamine levels, we will call the veteran and start them on thiamine tablets if they haven't already been started on them. We will notify their primary care doctor as well to ensure ongoing thiamine repletion after the study has concluded.

Withdrawal of Participants

We do not anticipate withdrawing participants from our study without their consent. Participants may withdraw from the study voluntarily at any time by in person meeting or telephone contact with study managers. The Principal Investigator also reserves the ability to early exit subjects from the study at any time in the event a subject is non-compliant with study visits any other component of the study. This will be exercised at the discretion of the PI only after multiple contact attempts have been made and a certified letter sent to the subject.

Approach to Analysis:

All data will be analyzed by a statistician affiliated with the VA research department trained biostatistician. The data will be analyzed using the statistical software SAS on the VA Informatics and Computing Infrastructure (VINCI).

15.1 Prospective cohort study to determine the prevalence and risk associations of TD.

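### Section 10.3 gives a repeat thiamine course after any incomplete first course, the risk section discontinues thiamine after any adverse reaction, and nothing says which governs when a reaction is the reason for stopping.

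*Combined protocol and SAP*

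**What the plan says.** Section 10.2 sets the length of the oral course: "we will provide a prescription for thiamine replacement 100 mg orally daily for two weeks". Section 10.3 then deals with Veterans who reach visit 3 without having finished it: "If a participant failed to complete the 2 weeks of replenishment, we will provide another 2-week course of replenishment and reschedule this visit". The sentence is triggered by non-completion alone and does not distinguish reasons.

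The risk section, under Protection Against Risk, has its own rule: "Any adverse reactions to parenteral or oral thiamine repletion will be recorded and replenishment discontinued". It sets no severity threshold and does not address restarting.

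The end of participation is described in the timeline section only for those who finish: "For Veterans with symptoms of TD their participation will be complete after taking thiamine for 2 weeks and attending visit 3". No separate path is given for a Veteran taken off thiamine early.

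**The concern.** Both rules are unqualified and neither refers to the other. A Veteran whose thiamine is stopped for a reaction on, say, day 5 has not had two weeks of it. Read literally, the risk section ends treatment and section 10.3 provides another course. Staff running visit 3 from section 10.3 alone are not told to ask why the course was incomplete before acting.

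Two things are at stake. The first is the safety instruction itself, which should not depend on what staff infer was meant. The second is the outcome. Section 15.1 defines the primary outcome by low or low-normal biomarkers together with symptoms that respond to thiamine, and section 10.3 rates that response at visit 3 in two categories only. The documents do not say how a Veteran who was stopped for a reaction and never completed a course is to be classified.

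**Working it through.** No figure in the plan is in dispute, so the check is a comparison of texts followed by a sizing calculation.

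**Do both rules apply to the same Veteran?**

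| | Section 10.3 | Protection Against Risk |
|---|---|---|
| Trigger | Two-week course not completed | Any adverse reaction, oral or parenteral |
| Action | Another two-week course; visit 3 rescheduled | Reaction recorded; thiamine stopped |
| Exceptions stated | None | None |
| Reference to the other rule | None | None |

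The course is two weeks (section 10.2). A stop for a reaction before day 14 meets both triggers, and the two actions are incompatible.

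**Does another section settle it?**

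- Withdrawal of Participants covers voluntary withdrawal and early exit "in the event a subject is non-compliant with study visits any other component of the study". Reactions are not mentioned.
- The safety-monitoring section says that named staff "will monitor Veterans prescribed thiamine repletion and report any new or unusual symptoms to the IRB". That is monitoring and reporting, with nothing on restarting.
- The consent section and the dosing text in section 10.2 contain no exception.

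So no section states an order of precedence.

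**How many Veterans?** Inputs:

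- Side-effect rate below 1% (safety-monitoring section), used as r = 0.01.
- 63 expected TDD cases (section 15.1). This agrees with 25% of the 255 Veterans left after drop-out: 0.25 × 255 = 63.75.
- 255 after drop-out and 300 enrolled (Sample Size).

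The number who will be treated is not stated. Treatment starts empirically on symptoms, so it may exceed 63. Treating all 255 or all 300 is an assumption made to show the range.

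Expected count = n × r; probability of at least one = 1 − (1 − r)^n, taking Veterans as independent.

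| n treated | Expected count | P(at least one) |
|---|---|---|
| 63 | below 63 × 0.01 = 0.63 | below 1 − 0.99^63 = 0.469 |
| 255 | below 255 × 0.01 = 2.55 | below 1 − 0.99^255 = 0.923 |
| 300 | below 300 × 0.01 = 3.0 | below 1 − 0.99^300 = 0.951 |

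The number under both rules is smaller still, because the reaction must also occur before the course ends.

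**Effect on the prevalence estimate.** Section 15.1 divides cases by all enrolled. One Veteran classified differently moves the estimate by 1/300 = 0.33 percentage points, and three move it by 3/300 = 1.0 point. The plan's stated precision is ±5.4 points.

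**The case against.** The strongest reply is that the two sentences can be read together. Failing to complete a course is ordinary language for missed doses, while discontinuation is an act that follows a reaction. On that view section 10.3 is a scheduling rule that was never meant to reach a Veteran taken off the drug. This is plausible, and a reader should not infer that the protocol intends re-exposure after a reaction. But the restriction is not written, and a safety instruction should not need it to be supplied.

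The protocol also has partial safeguards. Reactions must be recorded, treated Veterans are monitored, and the survey repeated at visit 3 asks about medication compliance. These make it likely that a reaction would be known. They do not require the reason for non-completion to be established before another course, and they do not say which rule then applies.

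Several stronger readings are tempting and are not supported:

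- A reader might infer that the notice to primary care "to ensure ongoing thiamine repletion after the study has concluded" is a further rule to re-dispense. It is a notification about care after the study. The study's own call to start tablets is limited to Veterans not already started.
- A reader might infer that the repeat course re-exposes Veterans to a material risk of anaphylaxis or angioedema. Those reactions are listed for parenteral or IV thiamine. The two-week course is oral, and the protocol describes similar effects with oral thiamine as far less common.
- A reader might infer that a Veteran rated at the rescheduled visit is rated without a full course. One who completes the repeat course has had two weeks of thiamine. The gap concerns only those who never complete one.

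**Conclusion.** The conflict of wording is real and the point is minor. As written, a Veteran stopped for a reaction before the end of the course is subject to two incompatible instructions, and no section resolves them.

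Fewer than 0.63 such Veterans are expected if 63 are treated, and fewer than 3 if all 300 are. A reader might take 3 as a ceiling; it is an expected count under the assumption that everyone is treated, and the actual number could be higher or lower. The sizing rests on the protocol's own rate of under 1%, which the documents do not break down by route. Any effect on the prevalence estimate is small beside the stated precision. The case for acting rests on a clear safety instruction and a defined outcome category, not on numbers.

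**What to change.** Reconcile section 10.3 with Protection Against Risk so that one stated rule covers non-completion caused by an adverse reaction. Which rule governs is a clinical decision for the sponsor, and this review takes no position on it.

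In section 10.3, require the reason for non-completion to be recorded before any further course is provided.

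In the analysis section, state that Veterans stopped for a reaction without completing a course are reported as a separate category and are counted neither as thiamine-responsive nor as non-responsive. Because the prevalence denominator is all enrolled, give their number beside the estimate.

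The cost is one or two sentences in an amendment and one field on the visit 3 form, with no added visits or staff.

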To obtain consent the research coordinator will approach the Veteran in their hospital room and ask if they wish to hear about the research we are conducting. If they are willing, they will describe, in plain English, the health effects of thiamine deficiency and the current knowledge deficit of what percentage of hospitalized Veterans suffer from it. We will confirm capacity utilizing the format of the U-ARE protocol⁴⁵. We will emphasize that participation is wholly voluntary and that they may stop participating at any time without penalty. We will discuss the fact that this research is designed to measure how often hospitalized Veterans suffer from thiamine deficiency which may result in the improvement of diagnosis and treatment of this condition in the Veteran population. We will describe the study procedures which will include several interviews by study staff, extra blood work which will be timed to coincide with routine blood work where possible, targeted physical examination, possible prescription of thiamine replacement. Lastly there may be a single follow up visit after treatment which will include interview, physical exam, and repeat blood draw. The total duration of participation will be four weeks or less. We will describe the fact that Veterans whom we suspect have TD based on their symptoms and/or physical exam will be prescribed oral thiamine replenishment and followed for symptom improvement. There will be no blinding of participants so that if thiamine is prescribed, they can be assured they are provided the vitamin and not a placebo. We will describe the possible risks of bleeding or bruising from phlebotomy. We will discuss the potential outcomes if the deficiency is left untreated such as worsening memory, weakness, falling, difficulties with eyesight, heart failure, nerve damage and in extreme cases death. There are no alternative treatments for TD besides vitamin replacement. If during participation in the study, we discover other vitamin or nutritional deficiencies, we will notify the patient's primary care provider to address these deficiencies. There will be no genetic material collected or stored because of this study. The consent form will also provide all participants with the principal investigator's and study coordinator's contact information to answer any questions that arise later.

Data Collection Procedures:

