10 STUDY INTERVENTIONS

Table 3: Study procedure schedule of evaluations

	Visit 1- early hospitalization	Visit 2 – late hospitalization	Visit 3 – after 2 weeks of thiamine repletion
Chart review for social and medical histories	X		
Symptom and function survey		X	X
Targeted physical exam		X	X
Nutritional history		X	
Lab draw for thiamine biomarkers	X		X
Blood draw for prealbumin , others as needed	X		
Thiamine repletion	X ¹	X ²	

1. For select patients with WE or severe symptoms of thiamine deficiency 2. all others

10.1 Visit 1 – initial hospital encounter: The Veteran's chart will be reviewed for acute and chronic medical problems, habits, and social history. We will schedule lab testing (as described below) to coincide with routine morning blood draw to avoid additional phlebotomy. For those who present with symptoms of Wernicke's encephalopathy (WE) which requires urgent parenteral thiamine replacement, we will perform our history and exam promptly and advise the primary inpatient treatment team to initiate therapy if they meet the Caine criteria⁴⁶ for WE. For all others who do not have evidence of WE, we will proceed to visit 2.

Thiamine biomarker and other micronutrient assessment: Fasting plasma thiamine levels and whole blood ThDP will be ordered for collection by lab personnel as soon as feasible after consent is obtained from the Veteran. We will also order blood levels of vitamins B12, D, and folic acid as well as prealbumin if not done via routine care within the preceding four weeks. In addition, we will extract albumin, complete blood count, and magnesium as ordered by the primary team as part of routine care. There will be no genomic sequencing, in whole or in part, as part of this analysis. Blood specimen will be collected as part of routine medical care by laboratory personnel. Lab tests not routinely run in our local laboratory will be sent out to reference labs per the usual practice of the Department of Pathology. There will be no direct handling of blood specimen by the research team. Results of the lab tests will be available in a participant's electronic medical record and will be extracted by the study coordinator and stored in a de-identified database. If they have been prescribed thiamine replenishment and the thiamine lab values are lost, we will include the remaining data gathered in the study.

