clinical test; ophthalmoplegia and nystagmus using the “H” test; evaluations of ataxia, peripheral neuropathy, deep tendon reflexes, and muscle strength using the Medical Research Counsel Adaptation B scale. We will assess for signs of cardiovascular dysfunction such as pulmonary or peripheral edema and tachycardia, and GI signs such as decreased bowel tones. We will assess physical signs of malnutrition including muscle and fat loss and trends in body weight. We will review any existing radiologic studies for evidence of abnormal brain imaging, echocardiogram results, pulmonary edema, or ileus for example.

For patients with severe symptoms such as inability to ambulate, or WE, we will advise the primary treatment team to begin high dose intravenous (IV) thiamine replenishment at 400 mg every eight hours for nine doses while inpatient. In this group we will then prescribe oral thiamine 100 mg once a day after IV therapy is complete until visit 3. For patients with mild-moderate symptoms that could be due to TD, the research pharmacist will process and dispense oral thiamine 100 mg once daily at hospital discharge. If the patient is discharged when the research pharmacist is not at the hospital, the research pharmacist will mail it to the patient on the next business day. Patients who are discharged to skilled nursing facilities, or any other rehabilitation facility, will be contacted by the research team and be medically advised to supplement the patient with oral thiamine 100 mg. We anticipate return of lab biomarker results 7-10 days after they are drawn at which point any individual not identified by clinical screening to have TD will be contacted and oral replenishment initiated. As with the symptom and function survey we will record these findings on a government furnished computer with a paper record as backup.

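### Moving Visit 3 for participants who do not complete two weeks of thiamine makes the timing of the response assessment depend on adherence, and can break the stated four-week participation limit

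*Combined protocol and SAP*

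**What the plan says.** Table 3 (section 10) has one assessment after treatment, headed "Visit 3 – after 2 weeks of thiamine repletion". The symptom and function survey, the examination and the thiamine biomarkers are repeated there. Section 10.3 says that the Veterans concerned "will be seen at a follow-up visit 3 after two weeks of thiamine replacement", and adds: "If a participant failed to complete the 2 weeks of replenishment, we will provide another 2-week course of replenishment and reschedule this visit". It provides for no assessment at the original date, gives no visit window and does not define completion. Sections 15.1 and 15.2 have no analysis rule for a deferred visit.

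Section 15.1 defines a case by low or low-normal biomarkers together with symptoms that respond to thiamine, and divides by everyone enrolled. Section 15.2 uses the split into responsive and non-responsive symptoms to choose biomarker cut-points.

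On duration, Informed Consent Process says "The total duration of participation will be four weeks or less", and Study Duration/Study Timeline says "For Veterans with symptoms of TD their participation will be complete after taking thiamine for 2 weeks and attending visit 3".

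Two other rules bear on non-completers. Withdrawal of Participants lets the principal investigator "early exit subjects from the study at any time in the event a subject is non-compliant with study visits any other component of the study", but only after repeated attempts at contact and a certified letter. Risk to Participants says that thiamine is discontinued after an adverse reaction; section 10.3 makes no exception for someone who stopped for that reason.

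**The concern.** Response is judged at one visit, and the date of that visit depends on adherence. Participants are recovering from an illness that put them in hospital, they know that they are taking thiamine, and there is no untreated comparison. Weakness, poor appetite, edema and low mood can improve with recovery alone. A participant who did not complete the course has more time to recover before being judged, and any improvement is read as response. If that participant does not return for the rescheduled visit, no outcome exists at all, although one could have been recorded at the planned date. Both effects reach the primary prevalence estimate and the cut-points of Aim 2.

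Separately, the participation length described at consent does not allow for the second course.

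**Working it through.** **Inputs.** From the documents: course length 14 days (10.3); participation limit 28 days (Informed Consent Process); biomarker results 7 to 10 days after the draw, with thiamine then started in those not already identified clinically (10.2); 300 enrolled and a precision of ±5.4 points (15.1). Not given: H, the days from consent to first dose, and k, the day of the first course on which non-completion is found. H is rarely zero. Of Visit 2, section 10.2 says "In most cases we anticipate this will occur just prior to hospital discharge", oral thiamine is dispensed at discharge, and if the pharmacist is away "the research pharmacist will mail it to the patient on the next business day".

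**1. The plan's own figure.** Planned path = H + 14 days. This is within 28 whenever H ≤ 14. For those started on a laboratory result it is 7 + 14 = 21 to 10 + 14 = 24 days from the draw. The four-week statement is therefore consistent with the path on which the course is completed.

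**2. Time from first dose to assessment.** Completers: about 14 days. Non-completers: k + 14 days, which is always longer. With k = 7 it is 21 days; with k = 14 (found at the planned visit) it is 28 days. No adherence check is scheduled before Visit 3, so k = 14 is the likely case.

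**3. Total participation on the deferred path** = H + k + 14 days.

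| Non-completion found | Total | Exceeds 28 days when |
|---|---|---|
| k = 4 | H + 18 | H > 10 |
| k = 7 | H + 21 | H > 7 |
| k = 14 | H + 28 | H ≥ 1 |

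At k = 14, the total is 29 days for H = 1, 33 for H = 5 and 38 for H = 10. Those started on a laboratory result reach 7 + 28 = 35 to 10 + 28 = 38 days from the draw.

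**4. Bias, as an illustration only.** The documents give no non-completion rate and no rate of improvement without thiamine. Assume that a proportion q improves in any two weeks regardless of thiamine. Doubling the wait adds [1 − (1 − q)²] − q: 9 points for q = 10%, 16 for 20%, 25 for 50%. Assume 60 to 150 treated, of whom 10 to 30% do not complete.

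- Low end: 60 × 0.10 × 0.09 = 0.5 extra responders, or 0.2 points of prevalence on 300.
- High end: 150 × 0.30 × 0.25 = 11 extra responders, or 3.8 points.

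This overstates the upward effect: it treats every non-completer as unable to respond truly, and it ignores the biomarker condition for a case. In the other direction, each true case lost after rescheduling counts as a non-case and lowers prevalence by 1/300 = 0.33 points.

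The plan's calculation of 81% power with 255 subjects is not affected.

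**The case against.** The strongest defence is the case definition. Section 15.1 requires improvement with adequate replenishment, and someone who has not completed the course has not had the planned amount. Another course before judging serves that definition. Classifying everyone at the planned date would label some deficient but under-treated participants as non-responders, which would lower prevalence and blur the cut-points. This stands, and it is why the planned-date assessment should not replace the later one as the main classification.

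Section 10.2 also delays Visit 2 until the acute illness has stabilized, to limit misclassification. That reduces improvement due to recovery after baseline but does not equalize the time over which it can occur.

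Several stronger readings are tempting, and the documents do not support them:

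- *The bias is always upward.* Loss after rescheduling works downward, because the denominator is everyone enrolled.
- *Every rescheduled participant exceeds four weeks.* Not if H + k ≤ 14.
- *Courses may be repeated without limit.* The text speaks of one further course.
- *The investigator freely chooses who is re-treated and who leaves.* The further course is stated as something that will be provided, and early exit has the safeguard of contact attempts and a certified letter.
- *Data collection at the planned date is ruled out.* The plan is silent. The survey includes a question on medication compliance, so non-completion might come to light during that very survey. But nothing requires the findings to be kept and used.

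**Conclusion.** The concern holds in a limited form. Section 10.3 makes the interval to the only response assessment depend on adherence: about 14 days in completers, k + 14 in non-completers, and 28 when non-completion is found at the planned visit. No assessment is provided for at a common time, and no analysis rule covers the difference. The net direction and size of the resulting bias cannot be derived from the documents; the 0.2 to 3.8 points above rest wholly on assumed rates and describe one direction only.

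The conflict over duration needs no assumption about recovery. When non-completion is found at the planned visit, participation is 28 + H days, which contradicts the four-week statement for any H of one day or more. Whether it happens in a given case depends on when non-completion is discovered.

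This should be changed before more follow-up accrues, because a planned-date assessment that was not recorded cannot be recovered at analysis.

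**What to change.** 1. **Section 10.3.** For every participant started on thiamine who is due Visit 3, carry out and record the survey and the standardized examination at the originally planned date, whether or not the course was completed. Record the doses taken and the reason for non-completion.
2. **Sections 15.1 and 15.2.** Keep the assessment after the completed course for the main classification. Add a sensitivity analysis of prevalence and of the cut-points using the planned-date assessment, and report the time from first dose to each assessment.
3. **Withdrawal of Participants.** State that non-adherence to thiamine alone is not a ground for ending outcome data collection.
4. **Informed Consent Process and Study Duration/Study Timeline.** Correct the stated participation length so that it covers the rescheduled path.
5. **Section 10.3 and Risk to Participants.** Reconcile the further course for non-completers with discontinuation after an adverse reaction. Whether a further course is given is for the sponsor to decide; none of these changes depends on it.

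The cost is protocol and consent wording, one more analysis, and one additional 60 to 90 minute assessment by existing staff for each non-completer who also has a later visit. Some planned-date assessments will follow a partial course; the recorded doses allow this to be examined.
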